Unique Protocol ID:	STUDY22070009
Brief Title:	Auditory Control Enhancement (ACE) in Schizophrenia (ACES)
Official Title:	Targeting the Auditory Control Network With Auditory Control Enhancement (ACE) in Schizophrenia
Secondary IDs:	R21MH128823 [U.S. NIH Grant/Contract Award Number]

Date: 02/06/2023

Study Protocol

Objectives

Although Auditory Control Enhancement (ACE) shows promise for treating AH, evidence for neural target engagement is needed to move forward with efficacy trials. In alignment with NIMH priorities, we plan to incorporate objective measures that test the delivered dosage and the proposed mechanism of action of the intervention and determine if the intervention target has been modulated. MRI and EEG afford parametric tests of biophysical and neurophysiological target engagement. In the proposed research, we will investigate biological target engagement in two sham-controlled experiments. In this study, we will determine whether tDCS of the auditory control network (rVLPFC anode and left TPJ cathode) leads to alterations in electric field and blood oxygenation level dependent (BOLD) response in the auditory control network during stimulation using Dual-Echo Echo Planar Imaging. Additionally, we will examine the degree to which ACE modifies behavioral and neurophysiological markers of cognitive control.

Design

Participants were randomly assigned to either active/verum or sham/placebo tDCS in a parallel-arm, 2x2 between-subjects repeated-measures design.

Methods

Prior to obtaining informed consent, participants underwent a telephone screening using a standardized script, which took approximately 15 minutes. After consent was obtained, a hearing test using the method of ascending limits (Grayson-Stadler GSI 17 Audiometer) was administered by [name] or trained research staff to rule out hearing loss, as this was essential for the auditory sensation experiment. This test was conducted in the research offices at Western Psychiatric Hospital and lasted about 15 to 30 minutes during the first session. Participants who did not pass the hearing test were advised to contact their primary care provider. Additionally, participants completed the Society of Magnetic Resonance Imaging's standardized MRI screening protocol prior to each MRI visit, which took about 10 minutes.

Demographic and medical history information was collected using a standard form during the first visit. Clinical and diagnostic assessments included the Structured Clinical Interview for DSM Disorders (SCID), which lasted approximately 1.5 to 2 hours. Additional assessments included the Positive and Negative Syndrome Scale (PANSS), Psychotic Symptoms Rating Scales (PSYRATS), and Global Functioning: Social and Role Scales.

These assessments collectively took about two hours, with PSYRATS administered both before and after ACE.

Neuropsychological testing involved the full MATRICS battery, targeting six cognitive domains affected in schizophrenia, and subtests from the WASI to assess general intelligence. The MATRICS battery took about one hour, and the WASI took approximately 30 minutes. Both were administered before and after ACE.

During the Auditory Control Enhancement (ACE) procedure, participants received transcranial direct current stimulation (tDCS) while performing a simple cognitive task. They were randomly assigned to receive either full-duration tDCS or a 30-second version (sham). [name] randomized participants based on their order of entry into the study. The study was single-blind, with participants unaware of their group assignment. Electrodes were placed over the right ventrolateral prefrontal cortex (anode; F8) and the left temporoparietal junction (cathode; CP5). tDCS sessions, conducted at WPH (Thomas Detre Hall and Oxford), were administered by [name] or trained staff. The current strength was set to 2.0 mA and was delivered for 30 minutes per session using saline-soaked sponge electrodes (10 cm² in size). Stimulation began two minutes before the task to assess discomfort, and skin sensation was checked verbally at least twice during stimulation. Participants were reminded they could withdraw at any time, and electrodes were never placed over the heart, eyes, or ears.

During tDCS, participants performed a cognitive task designed to train attention, working memory, and processing speed, lasting about one hour. The first ACE session involved a circular image with a single radius line, resembling a clock hand. Participants held a button to start each trial and released it when the line reached a target point. The task increased in difficulty by removing visual cues. ACE sessions 2 and 3 utilized simple button-response tasks and assessed reaction time and time estimation, respectively, using only basic shapes and lines.

EEG testing was led by [name] with support staff utilizing a 32-channel Starstim system. EEG amplifier bandpass was open (DC) to 166 Hz (24 dB/octave rolloff) digitized at 500 Hz. ASSR and AX-CPT stimuli were presented using Presentation software (NeuroBehavioral Systems). Timings of stimuli were confirmed by oscilloscope, and loudness confirmed with a sound meter and artificial ear canal. Sounds were created with NCH Tone Generator and edited in NCH Wavepad (NCH, Australia) and were presented over Etymotic 3A insert earphones. We measured differential 40Hz ASSR gamma power between attend/ignore conditions and beta-band oscillatory power in the AX-CPT as neurophysiological measures of auditory control network function. **ASSR.** Biphasic click trains were presented at 40 Hz (80 db, 500 ms duration, 1000 ms \pm 200 ms ISI). Subjects

once ignored the click trains and watch a silent video, and once listened to the clicks, pressing a button to click train presented at reduced intensity (75 db, 10% of trials) . We recorded 360 trials each under attend/ignore conditions. We assessed 35-45 Hz gamma power in frontocentral electrodes in attend and ignore conditions, as well as the difference between attend/ignore measurements. **AX-CPT** uses a combination of Latin letters as cues and probes following the established A-then-X rule. More specifically, the rule for the AX- is that 'X' is the target when directly preceded by the letter "A" trials, whereas a letter in any other sequence is a nontarget (e.g., AY, BX, and BY trials, where a B is any non-A cue, and a Y is any non-X probe). The AX and BX trials both require the representation and maintenance of the cue, or the goal of the task, to respond appropriately. BX trials tend to be the most sensitive to impairments in the ability to maintain the goal representation. That is, maintenance of the B cue is required to overcome the prepotent target response to the X on the trials when it does not follow an A. The most difficult trial is AY, given that goal focused maintenance of the A cue should produce a high expectancy of a subsequent X probe and preparation of a target response, resulting in increased errors or slowing on AY trials. 450 trials were presented in 6 blocks of 75 trials. The cue was presented for 500 ms with ISI of 1000 ms. Cognitive control was indexed by prefrontal beta-band activity following attention-alerting "B" trials. EEG was conducted both before and after ACE.

MRI data were collected using a 3T Siemens Prisma MRI system. Each participant underwent two 13-minute DE-EPI scans to map current flow during tDCS, along with T1 and T2-weighted structural imaging. MRI sessions lasted about one hour and were conducted before and after ACE. Participants completed pre- and post-scan questionnaires to evaluate their scanning experience. Those who reported smoking or consuming coffee within two hours of testing were asked to reschedule if the session could not be delayed.

Participants were asked to rate acceptability on a visual analogue scale, and to guess whether they received active or sham stimulation, using a forced choice questionnaire.

| | |
|---------------------|---|
| Unique Protocol ID: | STUDY22070009 |
| Brief Title: | Auditory Control Enhancement (ACE) in Schizophrenia (ACES) |
| Official Title: | Targeting the Auditory Control Network With Auditory Control Enhancement (ACE) in Schizophrenia |
| Secondary IDs: | R21MH128823 [U.S. NIH Grant/Contract Award Number] |

Date: 02/06/2023

Statistical Analysis Plan

Aim 1: H1. We will use General Linear Model (GLM) in SPM12 to assess the parametric modulation of 2nd -echo phase and magnitude data with the applied tDCS current as a regressor (as in Jog, Wang, et al., 2020). Phase data provide maps of tDCS-induced current tangential to the static (Bz) magnetic field of the MRI. Magnitude data provide BOLD response. We will test spatial correlation between the measured magnetic field and tDCS current modeled by SIMNIBS to assess overlap with target areas in rVLPFC and left TPJ.

Aim 2: H1. we will calculate retention, blinding, and acceptability scores with benchmarks of success being >80% study completion, high-moderate acceptability rating, and no-greater-than-chance ability to identify study condition. Additionally, t-tests will be used to compare acceptability between ACE and sham sessions.

Aim3: H1. Motion correction will be performed by realignment of the control and label image series to the M0 image. A structural correlation-based outlier rejection method will be applied to remove artifacts arising from outlier control-label pairs in ASL data. The perfusion-weighted maps will be calculated voxel by voxel from the average of signal differences between labeling and control images. The CBF will be quantified by $(6000 \cdot \lambda \cdot \Delta S \cdot \exp(-PLD/T1, \text{blood})) / (2 \cdot \alpha \cdot T1, \text{blood} \cdot SPD \cdot (1 - \exp(-\tau/T1, \text{blood})))$, where λ is the brain/blood partition coefficient in mL/g, ΔS is perfusion-weighted signal, $T1, \text{blood}$ is the longitudinal relaxation time of blood in seconds, α is the labeling efficiency, SPD is the signal intensity of a proton density-weighted image, and τ is the label duration. pcASL images will be registered to the T1-weighted anatomical image and normalized to MNI space. The CBF maps will be normalized by mean CBF value of GM and a 3D Gaussian filter will be applied. Comparisons will be restricted to rVLPFC and left TPJ ROIs, where 5000 permutations will be generated to identify statistically significant voxels pre- vs post-tDCS, controlling family-wise error rate ($p < 0.05$). H2. Data analysis will focus on (1) behavior assessed by reaction time and accuracy (d') measures from the AX-CPT, and on (2) attend-ignore difference in gamma-band oscillatory power measured from frontocentral electrodes in scalp-recorded ASSR (100-500 ms post-stimulus) as well as during the "preparation" window from 500-1000 ms following "B" trials of the AX-CPT. Spectral power will be measured using Morlet wavelet transforms with minimum width of 5 cycles, will be applied to elongated epochs at logarithmic steps from 4 to 80 Hz across the epoch. Maps of spectral measures will be baseline-corrected using a pre-stimulus baseline adjusted for >3 cycles per frequency to avoid edge effects. Four wavelet measures will be derived: Evoked power, the squared amplitude of oscillations that are phase-locked to stimulus onset; Total power, the average of power on each trial, which includes both evoked and "induced" (non-stimulus locked) responses; Induced power, calculated by removing

evoked from total power; and phase locking, the degree to which signals are in phase from trial to trial. We are most interested in total power in the AX-CPT, and evoked power ASSR; however, we will examine each of these measures as appropriate. Change scores will be calculated for each dependent variable as the difference between measures taken before and after each arm of the study (Active and Sham). We will compare these difference scores between active and sham arms of the study using repeated measures MANOVA with follow-up univariate RM-ANOVA and paired t-tests as appropriate. H3. Data analysis for H3 will follow the same procedures as H2; however, ASSR in the ignore condition will be the primary dependent variable in this analysis.

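### SAP Aim 1 H1 as written correlates a measured magnetic field with a modelled current; the two maps need not match even if the model is exact, so the result would not locate current at the targets.

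*SAP*

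**What the plan says.** The Protocol (Objectives) asks whether stimulation "leads to alterations in electric field and blood oxygenation level dependent (BOLD) response in the auditory control network during stimulation". The Protocol (Methods) describes "two 13-minute DE-EPI scans to map current flow during tDCS".

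The SAP, Aim 1 H1, then has three steps. The first is a GLM of the "parametric modulation of 2nd -echo phase and magnitude data with the applied tDCS current as a regressor". The second is a statement of what the phase images represent: "Phase data provide maps of tDCS-induced current tangential to the static (Bz) magnetic field of the MRI". The third is the step at issue: "We will test spatial correlation between the measured magnetic field and tDCS current modeled by SIMNIBS to assess overlap with target areas", where the areas are rVLPFC and left TPJ.

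Neither document says that the modelled current will be turned into a magnetic field, or the measured field into a current. For this correlation the SAP does not name the component or magnitude to be used, the handling of the field from the lead wires, a region-restricted test, or a threshold for success.

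**The concern.** MR phase responds to the component of the stimulation-induced field that lies along the static field, Bz. It does not respond to current density at the voxel. Bz at a point collects contributions from current everywhere in the head and in the leads, and it can be zero where the current is strongest, with lobes of opposite sign on either side. A correlation between a Bz map and a current map therefore has no natural benchmark: even a perfect model does not imply a high value.

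The third step is the only part of Aim 1 that ties the phase measurement to the two target areas. If it does not carry that meaning, Aim 1 has no stated analysis that supports a claim about where the current went. A weak correlation could be mistaken for poor delivery or a poor model, and a stronger one could owe something to how the leads were routed.

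**Working it through.** The plan gives no expected correlation, sample size or threshold for Aim 1, so there is no figure to reproduce. The check asks one question: if the SimNIBS current were exactly right and there were no noise, what would the planned correlation be?

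**Inputs from the documents.** Anode at F8, cathode at CP5, electrodes of 10 cm², and "The current strength was set to 2.0 mA" (Protocol, Methods). Current and electrode size are stated for the ACE sessions and are assumed here for the scans. The current strength cancels, because field and current density both scale with it.

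**Assumptions.** A homogeneous sphere of radius 9 cm, approximate electrode positions, z along the bore, and several invented lead routes.

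**Formula.** By Biot-Savart, B(x) = (μ0/4π) ∫ J(x′) × (x − x′) / |x − x′|³ dx′, taken over head and leads. Its z-component involves only Jx and Jy.

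**Simplest case.** Take a straight column of current with J(ρ) = exp(−ρ²/2). Then B(ρ) is proportional to [1 − exp(−ρ²/2)]/ρ.
- At ρ = 0, J is at its maximum of 1 and B is 0.
- B peaks near ρ = 1.6, where J has fallen to about 0.28.
- Over ρ < 3 the correlation of B with J is −0.32. For a single component of B it is 0, and for that component's absolute value −0.09.

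**Sphere, first setting.** J comes from the analytic solution for disc electrodes, and B from integration on a 3 mm grid, evaluated within 7.8 cm of the centre. As a check, curl(B)/μ0 returned J with r = 1.00 for each component and slope 1.006. In the table J is the magnitude of current density. The last two columns give the share of a 15 mm sphere under each electrode that lies in the top decile of absolute Bz.

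| Leads assumed | r, signed Bz with J | r, absolute Bz with J | Dice, top deciles of absolute Bz and J | Under F8 | Under CP5 |
|---|---|---|---|---|---|
| none | −0.10 | 0.07 | 0.22 | 4% | 4% |
| superior | −0.09 | 0.21 | 0.32 | 21% | 19% |
| posterior-superior | 0.04 | 0.19 | 0.34 | 29% | 24% |
| inferior-posterior | −0.01 | 0.12 | 0.34 | 26% | 30% |

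- Chance Dice for two unrelated top deciles is 2 × 0.1 × 0.1 / (0.1 + 0.1) = 0.10.
- In every row both spheres under the electrodes lie 100% in the top decile of J.
- J in the head is identical in all four rows. The lead field alone moves r for absolute Bz from 0.07 to 0.21.
- Using Jx, Jy or the in-plane magnitude of J instead gives r between −0.14 and 0.23.

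**Sphere, second setting.** With smoothed electrodes, a 4 mm grid and a mask at 0.8 × 9 = 7.2 cm, r is −0.14 for signed Bz and −0.01 for absolute Bz. Dice is 0.17 without leads and 0.10 with one assumed lead path. Other assumed routes at this mask give r of 0.05 to 0.20 for absolute Bz and Dice of 0.14 to 0.24.

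**Together.** r for absolute Bz with J runs from about −0.01 to 0.21, so at most 0.21² = 0.04 of the variance is shared. Dice runs from about 0.10 to 0.34. A like-for-like comparison, Bz against Bz computed from the same current and leads, gives r = 1 by construction.

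**The case against.** The strongest reply is that the SAP sentence is terse. It correctly calls the measured quantity a magnetic field, and the modelled current may be shorthand for the field predicted from that current. If so, the mismatch disappears and one added clause settles it. That reading is possible, but the text does not state it, and the sentence just before describes phase data as maps of current. Followed as written, the step compares unlike maps. Even under the kinder reading, agreement would validate the model, and dose at the targets would still be inferred from it.

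Second, field and current are physically linked. Overlap was above chance in most of the illustrations, and within the 15 mm spheres absolute Bz correlated with J at 0.27 to 0.46 in the first setting. This stands. A reader might infer that the measurement cannot say anything about delivered current, and that goes too far: the phase GLM can show a current-dependent field in the head, and the magnitude GLM addresses the BOLD half of the objective. Neither locates current at the targets.

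Third, a sphere without skull or CSF predicts nothing about this trial, and the figures move with mask, electrode shape and lead route. This also stands, which is why only ranges are given.

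Fourth, the like-for-like test has its own error. Neither document mentions recording lead positions, and lead route matters.

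Some stronger readings have no support in the documents. They do not label this correlation the primary test. They set no decision rule under which a low value would count as failed engagement. They do not say that voxels will be treated as independent; they do not say how the correlation will be tested at all.

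**Conclusion.** The concern holds for the correlation as the SAP words it. An exact model need not produce a high correlation between measured Bz and modelled current, so a low value would not show that current missed rVLPFC or left TPJ, and a high value would not locate it there. In the illustrations the correlation with absolute Bz stayed between about −0.01 and 0.21, with top-decile Dice of about 0.10 to 0.34 against 0.10 by chance.

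The conclusion rests on the Biot-Savart relation and on the literal SAP text. The size rests on a noise-free homogeneous sphere with assumed electrode positions and lead routes, and does not forecast the trial's values. The point should be corrected before the Aim 1 results are interpreted. It does not undermine the scans or the GLM.

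**What to change.** Revise SAP Aim 1 H1 as follows.

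1. Compute Bz for each participant from the SimNIBS current density by Biot-Savart. Model the lead wires, or state their assumed routes and vary them in a sensitivity analysis.
2. Correlate measured Bz with modelled Bz within each participant, and summarise the correlations across participants. Prespecify the statistic, the mask and how the result will be judged.
3. Report the modelled electric field in the rVLPFC and left TPJ regions, and label it as dose inferred from the model.
4. Reword the sentence on phase data to say that they map the current-induced field component along the static field.
5. If modelled Bz was intended all along, say so; steps 1 to 3 then become clarifications.

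The cost is SAP wording and one forward computation per participant; no new scans are needed. What remains is uncertainty from lead positions, which the sensitivity analysis can show but not remove.

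### The Aim 3 H1 perfusion (CBF) test is pre versus post with no stated active-versus-sham contrast, so a significant change could not be attributed to tDCS

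*SAP*

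**What the plan says.** **Design.** The Protocol's Objectives state that "we will investigate biological target engagement in two sham-controlled experiments". Its Design section adds: "Participants were randomly assigned to either active/verum or sham/placebo tDCS in a parallel-arm, 2x2 between-subjects repeated-measures design".

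**CBF (SAP, Aim 3 H1).** After preprocessing and normalisation to mean grey-matter CBF, the SAP states: "Comparisons will be restricted to rVLPFC and left TPJ ROIs". Within those regions, "5000 permutations will be generated to identify statistically significant voxels pre- vs post-tDCS, controlling family-wise error rate", at the 0.05 level. It names no arm factor, no arm-by-time term and no scheme for exchanging arm labels. It does not say whether sham scans are left out, pooled with active scans or analysed separately.

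**What separates the scans (Protocol, Methods).** MRI sessions took place before and after ACE. ACE is tDCS delivered while the participant performs a task intended to train attention, working memory and processing speed. Both arms do the task; the sham arm receives a 30-second version of the stimulation.

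**Where the SAP does compare arms.** Aim 2 compares acceptability between ACE and sham. Aim 3 H2 compares before-after change scores between active and sham, and H3 is said to follow H2. H1 is not mentioned there.

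**BOLD (SAP, Aim 1 H1).** The model assesses "parametric modulation of 2nd -echo phase and magnitude data with the applied tDCS current as a regressor". It adds: "Magnitude data provide BOLD response". The measured magnetic field is also correlated spatially with modelled current. No second-level active-versus-sham contrast is stated.

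**The concern.** A pre-post contrast estimates everything that changed between the two scans. Here that includes the cognitive training, familiarity with the scanner, changes in arousal, and tDCS. The sham arm was randomised so that the shared part could be subtracted. A CBF test without the arm contrast leaves that part in and labels the total as target engagement.

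Two features of the plan might seem to protect against this, but they do not:

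- Dividing by mean grey-matter CBF removes whole-brain shifts. It does not remove a regional change, and training of attention and working memory could plausibly produce one in a prefrontal region.
- Family-wise error control limits false positives across voxels when the true pre-post change is zero. If the true change is non-zero for a reason other than tDCS, a correct rejection of that null is still a wrong conclusion about tDCS.

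At stake is the claim that the study exists to test: whether stimulation modulates the target network.

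**Working it through.** **1. Reading the text.** The plan gives no sample size, power, effect size or SD, so there is no figure to reproduce. The inferential contrasts written in the SAP are:

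| Hypothesis | Contrast stated | Arms compared? |
|---|---|---|
| Aim 1 H1, phase and BOLD | signal on applied current, within scan | no |
| Aim 2 H1, acceptability | ACE versus sham | yes |
| Aim 3 H1, CBF | pre versus post | no |
| Aim 3 H2, behaviour and EEG | change, active versus sham | yes |
| Aim 3 H3, ASSR in the ignore condition | as H2 | yes |

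**2. Size of the problem for CBF (illustration).** Assumptions, none from the documents: tDCS has no effect; both arms share a drift of d SD of the change score; n per arm is 10, 15 or 20; tests are two-sided at 0.05 (the SAP does not state sidedness).

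The probability that the active-arm pre-post test is significant is P(|T| > t), where T is noncentral t with n − 1 df and noncentrality d√n, and t is the 97.5% point of central t. For n = 20 and d = 0.5 the noncentrality is 0.5 × √20 = 2.24, which gives 56.5%.

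| n per arm | d = 0.3, active pre-post | d = 0.5, active pre-post | active minus sham change |
|---|---|---|---|
| 10 | 13.6% | 29.3% | about 5% |
| 15 | 19.2% | 43.8% | about 5% |
| 20 | 24.7% | 56.5% | about 5% |

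The last column comes from 20,000 simulated trials per setting, including zero drift; all results lie between 4.7% and 5.2%. In the same simulations, pooling both arms into one pre-post test is worse: 25%, 36% and 46% at d = 0.3, and 57%, 75% and 87% at d = 0.5.

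**3. Does voxelwise error control change this?** A max-statistic permutation test was simulated with 100 voxels, pairwise correlation 0.5, drift in every voxel, 500 permutations and 400 runs. For n = 10, 15 and 20:

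- Pre-post in the active arm finds at least one voxel in about 16%, 27% and 37% of runs at d = 0.3, and 42%, 61% and 78% at d = 0.5.
- Active versus sham on change, permuting arm labels, does so in 3% to 7% of runs. The simulation error at a true 5% is √(0.05 × 0.95 / 400) = 1.1 percentage points, so this is compatible with the nominal level.

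**4. Cost of the between-arm contrast.** With n per arm and SD s of the change score, the standard error is s√(2/n) instead of s/√n, a factor of √2 = 1.41. For 80% power at two-sided 0.05 (normal approximation), with (1.960 + 0.842)² = 7.85:

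| Effect (SD of change) | Between arms: 2 × 7.85 / effect², per arm | One group: 7.85 / effect², in total |
|---|---|---|
| 0.5 | 63 | 32 |
| 0.8 | 25 | 13 |
| 1.0 | 16 | 8 |

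**The case against.** **The design already implies the contrast.** The protocol fixes an arm-by-time design, and the H2 text speaks of change scores for each dependent variable, which could be read to include CBF. A reader might go the other way and infer that the sham arm plays no part in the analysis. The documents do not support that: Aim 2, H2 and H3 all use it. What stands is narrower. The between-arm text sits under H2 after the EEG measures, only H3 adopts it, and its MANOVA, ANOVA and t-test methods differ from H1's voxelwise permutation test. Even on the generous reading, H1 would have two tests and no rule for which one decides.

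**The interval may not contain the training.** The SAP says pre versus post tDCS, while the protocol places MRI before and after ACE. If CBF were compared around stimulation within one session, training would drop out as an explanation. Time in the scanner and arousal would not, so the need for the arm contrast remains. The SAP should say which interval it means.

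**The percentages are assumed scenarios.** This is correct. They show how the false-positive rate behaves over a range and do not predict this trial. Nor does the SAP say that it would judge success by a significant active arm beside a non-significant sham arm.

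**Aim 1 is different in kind.** A reader might infer that time, habituation or task effects confound the Aim 1 maps in the same way. The documents do not support that. The regressor is locked to applied current, no in-scanner task is described, and the current waveform is not given. Phase is a direct physical reading of the field and is also checked against modelled current. Nor can the precision of a sham-arm coefficient be worked out, because the 30-second sham is described for ACE sessions and not for the scanner. What remains concerns BOLD magnitude only: sensation or other non-specific responses to current would also follow the regressor, and no sham contrast is written to remove them.

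**Conclusion.** The point holds for CBF and should be fixed before that analysis is run. As written, the H1 test cannot separate tDCS from anything else that changed between the scans, so it cannot support a sham-controlled claim of target engagement. That conclusion rests on the text alone.

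Its numerical size depends on assumptions about sample size and drift. Across the illustrated range (0.3 to 0.5 SD, 10 to 20 per arm), the chance of a spurious single-test result is roughly 3 to 11 times the nominal 5% (13.6/5 = 2.7; 56.5/5 = 11.3). With no shared drift there is no inflation.

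For Aim 1, the supportable statement is only that a second-level active-versus-sham contrast for BOLD magnitude is missing. It is a secondary point.

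**What to change.** **CBF, Aim 3 H1.** State that the primary test compares active with sham on each participant's post-minus-pre CBF map. Permute arm labels (5,000 permutations, as already planned), with max-statistic family-wise control at 0.05 over both ROIs together. Report within-arm pre-post maps as descriptive. State the sidedness and which two scans define pre and post.

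**BOLD, Aim 1 H1.** State what sham participants received in the scanner. If they were scanned with a sham waveform, fit the same nominal current regressor in both arms and compare ROI coefficients between arms. If that waveform includes a short period of real current, sham is not strictly a no-current reference, and the SAP should say so.

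**Cost.** The change is to SAP wording and analysis code. It needs no new data provided that perfusion scans exist in both arms; this should be confirmed, because the protocol's list of MRI sequences does not include pcASL. The real price is power. At an assumed 0.5 SD effect, 80% power takes 63 per arm (126 in total) against 32 for a one-group test, about four times as many. That is worth accepting, because the one-group test's extra power is not power to detect an effect of tDCS. If the available sample is small, report the between-arm estimate with its confidence interval and say that it is imprecise.

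### SAP Aim 3 H2 names only gamma power for the AX-CPT preparation window, while the protocol's AX-CPT marker is beta power, so no test of that marker is prespecified

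*SAP*

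**What the plan says.** The protocol's EEG paragraph (Methods) gives each task its own band: "We measured differential 40Hz ASSR gamma power between attend/ignore conditions and beta-band oscillatory power in the AX-CPT as neurophysiological measures". For the ASSR it adds limits and a site: "We assessed 35-45 Hz gamma power in frontocentral electrodes in attend and ignore conditions". For the AX-CPT it adds a region and an event: "Cognitive control was indexed by prefrontal beta-band activity following attention-alerting" B trials. It gives no beta limits in Hz and no list of prefrontal electrodes.

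The SAP (Aim 3, H2) puts both tasks into one phrase. The outcome is the attend-minus-ignore difference in "gamma-band oscillatory power measured from frontocentral electrodes in scalp-recorded ASSR (100-500 ms post-stimulus) as well as during the" preparation window, which runs from 500 to 1000 ms after B trials of the AX-CPT. No separate band or electrode set follows for the AX-CPT.

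On method, the SAP states: "Spectral power will be measured using Morlet wavelet transforms with minimum width of 5 cycles", and that these "will be applied to elongated epochs at logarithmic steps from 4 to 80 Hz across the epoch". It derives four wavelet measures. Total power is of most interest for the AX-CPT and evoked power for the ASSR, and the others may be examined where suitable. It names no band at that point. The word beta does not appear in the SAP. Both documents carry the date 02/06/2023, and neither is said to supersede the other.

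**The concern.** The protocol's objectives include examining whether ACE changes behavioural and neurophysiological markers of cognitive control. Prefrontal beta after B trials is the only EEG measure that the protocol explicitly calls an index of cognitive control. The SAP is where that measure should become a dependent variable, and it does not.

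Two things are at stake. First, an analyst who follows the SAP would either analyse gamma in the AX-CPT window or find that the sentence cannot be applied to that task. Second, two documents of the same date support different bands, so beta or gamma could be reported depending on which looks better. That freedom matters more here because only participants are described as unaware of their assignment.

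**Working it through.** The documents give no sample size, power, effect size or standard deviation for this outcome, so there is no stated figure to reproduce. The check is mainly a comparison of texts, followed by two short calculations on the wavelet transform.

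**1. The documents side by side**

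| Item | Protocol, ASSR | Protocol, AX-CPT | SAP H2, as worded |
|---|---|---|---|
| Band | Gamma, 35-45 Hz | Beta (stated twice) | Gamma only |
| Site | Frontocentral | Prefrontal (stated once) | Frontocentral only |
| Contrast | Attend, ignore and their difference | After B trials (stated once); no attend/ignore conditions described | Attend minus ignore |
| Window | None given for the power measure | None given for the power measure | 100-500 ms (ASSR); 500-1000 ms after B trials (AX-CPT) |

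The SAP's band, site and contrast match the protocol's ASSR column. Only the second window belongs to the AX-CPT.

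**2. Possible readings of the SAP sentence**

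- *The whole phrase governs both tasks.* The AX-CPT outcome is then an attend-minus-ignore gamma difference. It cannot be computed, because the protocol describes no such conditions for that task.
- *Gamma and the site carry over, but the contrast does not.* The AX-CPT outcome is then frontocentral gamma. This can be computed, but it is not the protocol's marker.
- *Gamma, site and contrast all belong to the ASSR.* The AX-CPT then has a window and a preference for total power, but no band and no electrode set.

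None of the three yields a prespecified beta outcome.

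**3. Can beta be obtained from the planned transform?**

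The documents give no beta limits; 13-30 Hz is assumed. That range lies inside 4-80 Hz and does not overlap 35-45 Hz. If width is read as total wavelet length = cycles / frequency, five cycles last 5/13 = 0.385 s at 13 Hz and 5/30 = 0.167 s at 30 Hz. Both are shorter than the 0.5 s preparation window. Beta can be estimated.

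**4. How much beta would a gamma analysis pick up?**

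This step reads five cycles as centre frequency divided by spectral SD, so SD = f0/5. The SAP does not define width, so this is an assumption. The power response at frequency f is exp(-((f - f0)/(f0/5))²).

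| Oscillation | f0 = 35 Hz (SD 7) | f0 = 40 Hz (SD 8) |
|---|---|---|
| 20 Hz | exp(-(15/7)²) = 0.010 | exp(-(20/8)²) = 0.0019 |
| 25 Hz | exp(-(10/7)²) = 0.130 | exp(-(15/8)²) = 0.030 |
| 30 Hz | exp(-(5/7)²) = 0.60 | exp(-(10/8)²) = 0.21 |

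Five is the SAP's minimum number of cycles; more cycles narrow the response and pass less.

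**5. How much choice is left open?**

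With total power only, two bands give 2 candidate AX-CPT outcomes, or 4 if the site is also open. With all four wavelet measures, the counts are 2 × 4 = 8 and 2 × 2 × 4 = 16. These outcomes are correlated, so the counts describe freedom of choice and are not a multiplicity factor.

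**The case against.** The strongest defence is that the sentence is a drafting slip and not a change of band. The attend/ignore contrast makes no sense for the AX-CPT, so a sensible analyst would not apply the phrase literally. The wide transform and the separate remark on total power in the AX-CPT are both compatible with beta. This is plausible, and it limits the charge: a reader might infer that the trial is committed to testing the wrong band, but the sentence is too loosely built to show that. The defence does not close the gap. Compatibility with beta does not name beta as the dependent variable, and a sentence that cannot be applied to one of its two tasks needs rewriting.

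A reader might also infer that the SAP picks the wrong electrode site. The documents do not support this. Frontocentral may attach to the ASSR alone, where it agrees with the protocol. The AX-CPT site would then be unspecified.

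A third tempting inference is that a beta effect would be lost or almost invisible. It would not be lost, because the transform covers beta. Nor would all of it be invisible to a gamma analysis: near 30 Hz the calculation gives 21% to 60% of power passed. The low figures apply to low and middle beta only. Even so, partial leakage into a gamma estimate is not a test of beta.

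Finally, the consequence is bounded. The protocol introduces the cognitive-control markers as an addition to the electric-field and BOLD questions. The AX-CPT behavioural outcomes and the ASSR outcome in H2 are untouched. This stands as a limit on scope.

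**Conclusion.** The two documents conflict on the band of the AX-CPT EEG outcome, and nothing else in them resolves it. As written, the SAP has no prespecified test of the protocol's beta marker and leaves the band open to choice after results are seen. This rests on the text alone and holds under each reading considered.

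The defect is one of prespecification, not of measurement. The size of the leakage depends on two assumptions, beta at 13-30 Hz and f/SD = 5. Under them, a gamma analysis at 35-40 Hz captures 0.2% to 1% of power at 20 Hz, 3% to 13% at 25 Hz and 21% to 60% at 30 Hz. The site question is an ambiguity to settle, not a demonstrated error.

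**What to change.** Split the H2 sentence into two dependent variables:

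- **ASSR:** attend-minus-ignore evoked power, 35-45 Hz, frontocentral electrodes, 100-500 ms after stimulus.
- **AX-CPT:** beta-band total power over a named prefrontal electrode set, 500-1000 ms after B trials.

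State the beta limits in Hz and list the electrodes, since neither document gives them. Fix both before the EEG data are analysed by arm. That is the relevant milestone, because only participants are described as unaware of assignment. Define what a five-cycle width means. If AX-CPT gamma is kept, report it as exploratory; if it is the intended outcome, say so and justify it as a departure from the protocol.

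The cost is SAP wording. No new data or processing are needed, because the 4-80 Hz transform already covers beta.
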